5.5.5 Storage and Accountability

[REDACTED].

The Investigator must designate a research pharmacist or other staff member to be unblinded and maintain an inventory record of drugs received and dispensed. Used vials should be retained for drug accountability by the site monitor, unless prohibited by local procedures, in which case an alternative drug accountability process will be agreed upon with the Sponsor. Additional details on study drug handling will be provided in the Pharmacy Manual.

Forms will be provided to facilitate the inventory control. These forms must be used unless the Investigator has previously established a system that complies with local regulations and is approved by the Sponsor. The study drug must be dispensed only at the institution(s) specified on form Food and Drug Administration (FDA) 1572.

Upon completion or termination of the study and after inventory by a Sponsor-designated monitor, it will be determined if unopened drug is to be sent to the Sponsor in the original containers or is to be destroyed on site. Residual solutions must be discarded after use, as outlined in the Pharmacy Manual and per approved institutional procedures.

5.6 Prior and Concomitant Medications and/or Procedures

5.6.1 Excluded Medications and/or Procedures

Systemic corticosteroids at a dose equivalent to >20 mg/day of prednisone (including every other day dosing of >40 mg equivalent) or any immunosuppressive medication or biologic for the treatment of inflammatory or autoimmune disease is prohibited.

5.6.2 Restricted Medications and/or Procedures

Subjects may continue on an oral macrolide treatment (eg, azithromycin, erythromycin, or clarithromycin), hyper tonic saline, mucolytics, bronchodilator medications, or oral corticosteroids with a stable dose as long as it was not initiated within the 30 days prior to Screening.

5.6.3 Documentation of Prior and Concomitant Medication Use

Medications used within 30 days prior to Screening will be recorded. The coronavirus disease 2019 vaccination status (including type of vaccine and administration date[s]) of all subjects will be recorded as a prior (if received prior to dosing) and/or concomitant medication in the eCRF.

Any treatment given in addition to the study drug during the study will be regarded as a concomitant medication and must be recorded on the appropriate eCRF.

Any relevant medications received in the 28 days prior to randomization must be recorded on the appropriate eCRF, along with the reason for use, dates of administration, and dosages.

Concomitant medications, including over-the-counter medications and herbal supplements, should be kept to a minimum during the study. However, if these are considered necessary for the subject's welfare and are unlikely to interfere with the study drug, they may be given at the discretion of the Investigator and recorded in the subject's source documents and the eCRF.

5.6.4 Contraception

Women of childbearing potential must agree to use a highly effective method of birth control from the list below (defined as those, alone or in combination, that result in a low failure rate, ie, less than 1% per year when used consistently and correctly). Double barrier methods (a combination of condom with cap, diaphragm, or sponge with spermicide) are not considered highly effective. Childbearing potential is defined as being fertile following menarche and until becoming post-menopausal, unless permanently sterile. Permanent sterilization methods include hysterectomy, bilateral salpingectomy, and bilateral oophorectomy.

Highly effective methods of birth control include:

- Combined (estrogen and progesterone containing) hormonal contraception associated with inhibition of ovulation (oral, intravaginal, transdermal);
- Progesterone-only hormonal contraception associated with inhibition of ovulation (oral, injectable, implantable);
- Intrauterine device;
- Intrauterine hormone-releasing system;
- Bilateral tubal occlusion;
- Vasectomized partner (provided that partner is the sole sexual partner and has received medical assessment of the surgical success); and
- Sexual abstinence. Sexual abstinence must be true abstinence which is the preferred and usual lifestyle of the subject. Periodic abstinence (eg, calendar, ovulation, symptom-thermal, post-ovulation methods), declaration of abstinence for the duration of the study, and withdrawal are not acceptable methods of contraception.

Birth control measures must be employed during the time of participation (beginning at the Screening Visit) in this study. Protections against pregnancy must be continued for at least 60 days after the last dose of study drug.

A man is considered fertile after puberty unless permanently sterile by bilateral orchiectomy. Male subjects with medical confirmation of azoospermia and/or infertility will be considered permanently sterile. A man who is fertile should use a condom during treatment and until 60 days after the last dose of study drug. Male subjects must refrain from donating sperm throughout the study and until 60 days after the last dose of study drug.

6 STUDY PROCEDURES

Study procedures will follow the Schedule of Assessments and Timing of Sample Collection and Procedures for the Treatment Period ([Appendix A](#)).

7 EFFICACY ASSESSMENTS

7.1 Efficacy Endpoints

The primary efficacy endpoint is sputum *P. aeruginosa* density as measured in sputum samples at 1 week after end of treatment for study drug (Visit 5/Day 17).

The phage recovery endpoint is based on AP-PA02 levels as measured in sputum and venous blood samples at time points specified in the Schedule of Assessments ([Appendix A](#)).

The exploratory endpoints include the following:

- Antipseudomonas antibiotic sensitivity of *P. aeruginosa* isolates at specified time points during the study;
- Change in *P. aeruginosa* density from Baseline;
- Change from Baseline of in vitro sensitivity of subject *P. aeruginosa* isolates to AP-PA02 and/or individual phage components;
- Change in spirometry from Baseline;
- Change from Baseline levels of sputum neutrophil elastase; and
- Change in quality of life as assessed by the following questionnaires:
 - Quality of Life-Bronchiectasis (QOL-B) Questionnaire;
 - Leicester Cough Questionnaire (LCQ); and
 - Saint George's Respiratory Questionnaire.

7.2 Sputum Culture

Sputum for microbiology will be processed at a central laboratory for all visits. Quantitative cultures and sensitivity will be performed. *P. aeruginosa* isolates obtained from sputum samples at all visits will be frozen for possible future genotyping analysis. No subject (human) samples will be retained for any genetic analysis.

Collection of sputum via spontaneous expectoration or induction will be performed per standardized methodology at the time points specified in the Schedule of Assessments and Timing of Sample Collection and Procedures for the Treatment Period ([Appendix A](#)). Induced sputum samples for culture will be required at Screening, Baseline, Visit 2/Day 5, Visit 3/Day 10, Visit 4/Day 11, Visit 5/Day 17, Visit 6/Day 24, and Visit 7/EOS/Day 38. Standardized sputum induction methodology will be detailed in the Study Manual.

For expectorated sputum collection, subjects may be asked to provide first morning samples expectorated before a given clinic visit or the subjects may provide the expectorated sputum sample during the clinic visit. Samples collected at home by the subject should ideally be collected prior to administration of any inhaled antipseudomonal antibiotic. Subjects will be provided sputum collection containers and insulated transport containers in which to carry their specimens to the clinic.

7.2.1 Antipseudomonal Antibiotic Sensitivity

Antipseudomonal antibiotic sensitivity will be tested by the central microbiology laboratory at the visits indicated in the Schedule of Assessments ([Appendix A](#)).

7.2.2 Sensitivity of *Pseudomonas aeruginosa* Isolates to AP-PA02

The change in *P. aeruginosa* isolate sensitivity to AP-PA02 between initiation of study drug and the last isolation of *P. aeruginosa* from sputum will be assessed as indicated in the Schedule of Assessments ([Appendix A](#)).

7.3 Sputum Phage Titer

Sputum for phage titer will be obtained as designated in the Schedule of Assessments and Timing of Sample Collection and Procedures for the Treatment Period ([Appendix A](#)). Induced sputum samples will be required on Visit 1/Day 1, Visit 2/Day 5, Visit 3/Day 10, Visit 4/Day 11, Visit 5/Day 17, Visit 6/Day 24, and Visit 7/EOS/Day 38. Sputum samples will be obtained in the morning on Visit 4/Day 11.

7.4 Blood Phage Titer

Blood for phage titer will be obtained as designated in the Schedule of Assessments and Timing of Sample Collection and Procedures for the Treatment Period ([Appendix A](#)). When blood samples are scheduled at time points when safety laboratories and phage titer samples are also to be collected, safety laboratory samples are to be collected first, followed by phage titer samples. Blood samples will be obtained in the morning on Visit 4/Day 11.

7.5 Urine Phage Titer

Urine samples for phage recovery will be obtained at the visits indicated in the Schedule of Assessments ([Appendix A](#)) using provided collection containers. Date and time will be recorded for each urine sample collection at the designated time points.

7.6 Change in Spirometry

Spirometry will be performed per American Thoracic Society/European Respiratory Society Standards^{28,29,30,31,32} and evaluated locally at the clinical study site. FEV₁, forced vital capacity (FVC), and forced expiratory flow between 25% and 75% of the FVC (FEF₂₅₋₇₅) will be collected. Actual liter values will be recorded. Details regarding spirometry procedures and standards will be included in the Study Manual.

7.7 Daily Symptom Diary

A standardized subject diary will be provided to each study subject to collect subject symptoms following the administration of study drug. Solicited symptoms assessed may include but are not limited to: difficulty breathing, cough, sputum production, color of sputum, hemoptysis, feeling feverish, and/or fatigue. The daily diary will be dispensed to study subjects starting at the Baseline Visit for all subjects. Subjects will be instructed to bring the diary to the clinic for each subsequent study visit for review and the diary will be collected at the End of Study Visit.

7.8 Biomarkers

Biomarkers, including sputum neutrophil elastase, will be tested by the central laboratory as indicated in the Schedule of Assessments and Timing of Sample Collection and Procedures for the Treatment Period ([Appendix A](#)).

7.9 Questionnaires

Subjects will complete questionnaires according to the Schedule of Assessments ([Appendix A](#)).

7.9.1 Quality of Life-Bronchiectasis Questionnaire

The QOL-B Questionnaire is a self-administered PRO measure designed specifically for subjects with bronchiectasis.³³ This PRO contains 37 items on 8 scales to assess respiratory symptoms, functioning, and health-related quality of life of subjects within the past week.

7.9.2 Leicester Cough Questionnaire

The LCQ is a 19 item self-completed quality of life measure of chronic cough which is responsive to change.³⁴ Subjects will respond to each item using a 7-point Likert response scale.

7.9.3 Saint George's Respiratory Questionnaire

The Saint George's Respiratory Questionnaire is a measure to assess impaired health and perceived well-being (quality of life).³⁵ The Saint George's Respiratory Questionnaire was designed to allow for comparative measurements of health and quantify changes in health following treatment. Scores of 3 components (symptoms, activity, and impacts [on daily life]) and total score will be evaluated.³⁶

8 SAFETY ASSESSMENTS

8.1 Adverse Events

An AE is defined as any untoward medical occurrence in a clinical investigation subject administered a pharmaceutical product, which does not necessarily have a causal relationship with this treatment. An AE can therefore be any unfavorable and/or unintended sign (including an abnormal laboratory finding), symptom, or disease temporally associated with the use of an investigational medicinal product, whether or not related to the investigational medicinal product. All AEs, including observed or volunteered problems, complaints, or symptoms, are to be recorded on the appropriate eCRF.

AEs, which include clinical laboratory test variables, will be monitored and documented from the time of first dose of AP-PA02 or placebo until the EOS Visit. Subjects should be instructed to report any AE that they experience to the Investigator, whether or not they think the event is due to study treatment. Beginning at the date of the first dose of study drug, Investigators should make an assessment for AEs at each visit and record the event on the appropriate AE eCRF.

Wherever possible, a specific disease or syndrome rather than individual associated signs and symptoms should be identified by the Investigator and recorded on the eCRF. However, if an observed or reported sign or symptom is not considered a component of a specific disease or syndrome by the Investigator, it should be recorded as a separate AE on the eCRF. Additionally, the condition that led to a medical or surgical procedure (eg, surgery, endoscopy, tooth extraction, or transfusion) should be recorded as an AE, not the procedure itself.

Any medical condition already present prior to the first dose of the study drug should be recorded as medical history and not be reported as an AE unless the medical condition or signs or symptoms present at Baseline changes in severity, frequency, or seriousness at any time during the study. In this case, it should be reported as an AE.

Clinically significant abnormal laboratory or other examination (eg, ECG) findings that are detected during the study or are present prior to the first dose of study drug and significantly worsen during the study should be reported as AEs, as described below. The Investigator will exercise his or her medical and scientific judgment in deciding whether an abnormal laboratory finding or other abnormal assessment is clinically significant. Clinically significant abnormal laboratory values occurring during the clinical study will be followed until repeat tests return to normal, stabilize, or are no longer clinically significant. Abnormal test results that are determined to be an error should not be reported as an AE. Laboratory abnormalities or other abnormal clinical findings (eg, ECG abnormalities) should be reported as an AE if any of the following are applicable:

- If an intervention is required as a result of the abnormality;
- If action taken with the study drug is required as a result of the abnormality; or
- Based on the clinical judgment of the Investigator.

8.1.1 Adverse (Drug) Reaction

All noxious and unintended responses to a medicinal product related to any dose should be considered an adverse drug reaction. “Responses” to a medicinal product means that a causal

relationship between a medicinal product and an AE is at least a reasonable possibility, ie the relationship cannot be ruled out.

8.1.2 Unexpected Adverse Drug Reaction

An unexpected adverse drug reaction is defined as an adverse reaction, the nature or severity of which is not consistent with the applicable product information. For AP-PA02, the reference safety information is included in the Investigator's Brochure currently in force. The reference safety information will be reviewed yearly, and the periodicity of the review will be harmonized with the reporting period of the Development Safety Update Report.

8.1.3 Assessment of Adverse Events by the Investigator

The severity of all AEs should be graded according to the CTCAE version 5.0. For those AE terms not listed in the CTCAE, the following grading system should be used:

- CTCAE Grade 1: Mild; asymptomatic or mild symptoms; clinical or diagnostic observations only; intervention not indicated;
- CTCAE Grade 2: Moderate; minimal local or noninvasive intervention indicated; limiting age-appropriate instrumental activities of daily living;
- CTCAE Grade 3: Severe or medically significant but not immediately life-threatening; hospitalization or prolongation of hospitalization indicated; disabling; limiting self-care activities of daily living;
- CTCAE Grade 4: Life-threatening consequences; urgent intervention indicated; or
- CTCAE Grade 5: Death related to the AE.

Causality assessment

The relationship of an AE to the administration of the study drug is to be assessed according to the following definitions:

No (unrelated, not related, unlikely to be related) – The time course between the administration of study drug and the occurrence or worsening of the AE rules out a causal relationship and another cause (concomitant drugs, therapies, complications, etc) is suspected.

Yes (possibly, probably, or definitely related) – The time course between the administration of study drug and the occurrence or worsening of the AE is consistent with a causal relationship and no other cause (concomitant drugs, therapies, complications, etc) can be identified.

The definition implies a reasonable possibility of a causal relationship between the event and the study drug. This means that there are facts (evidence) or arguments to suggest a causal relationship.

The following factors should also be considered:

- The temporal sequence from study drug administration-

The event should occur after the study drug is given. The length of time from study drug exposure to event should be evaluated in the clinical context of the event.

- Underlying, concomitant, intercurrent diseases-

Each report should be evaluated in the context of the natural history and course of the disease being treated and any other disease the subject may have.

- Concomitant drug-

The other drugs the subject is taking or the treatment the subject receives should be examined to determine whether any of them might be recognized to cause the event in question.

- Known response pattern for this class of study drug-

Clinical and/or preclinical data may indicate whether a particular response is likely to be a class effect.

- Exposure to physical and/or mental stresses-

The exposure to stress might induce adverse changes in the recipient and provide a logical and better explanation for the event.

- The pharmacology and pharmacokinetics of the study drug-

The known pharmacologic properties (absorption, distribution, metabolism, and excretion) of the study drug should be considered.

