3.2 Study Indication

The indication for this study is management of NCFB subjects with chronic respiratory infections associated with *P. aeruginosa*.

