- Study Procedure-related TEAEs by maximum severity, overall and by SOC and PT
- TEAEs leading to permanent withdrawal of study drug, overall and by SOC and PT
- Study Drug-related TEAEs leading to permanent withdrawal of study drug, overall and by SOC and PT
- Study Device -related TEAEs leading to permanent withdrawal of study drug, overall and by SOC and PT
- Study Procedure -related TEAEs leading to permanent withdrawal of study drug, overall and by SOC and PT
- TEAEs which resulted in death, overall and by SOC and PT

If a subject has more than one event within a given SOC or PT at different severities, the maximum severity will be tabulated. For example, if a subject experiences two events with the same preferred term, but one was at moderate and the other at severe severity, the severe TEAE will be included in the tabulation. Severity is classified into five categories: mild, moderate, severe, life-threatening, and death.

An AE will be considered drug-related if the relationship attribution is 'possibly related', 'probably related', or 'definitely related' or designation is missing. AEs with a missing onset date, but with stop date either missing or on or after the date of first dose of study drug will be included as treatment emergent. All AEs will be listed in subject listing and summarized by numbers and percent of subjects by dose for each portion of the study separately. If a subject reports the occurrence of a particular event more than once, the most severe of those events will be included in the summary tables of TEAEs, and the most severe of the treatment-related events will be included in the summary tables of treatment-related events.

If the relationship to study drug, study device, or study procedure, is missing for an AE, the event will be assumed to have the maximum relationship (i.e., definitely), respectively. If the seriousness status is missing for an AE, the event will be assumed to be serious.

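### Protocol 8.1.3 gives no causality category to an event with compatible timing and another possible cause, although 8.1.1 counts that event as a reaction

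*Protocol*

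**What the plan says.** Protocol Section 8.1.3 gives a two-way causality scale.

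- **Yes** covers possible, probable and definite relationships. The time course must be "consistent with a causal relationship and no other cause (concomitant drugs, therapies, complications, etc) can be identified".
- **No** covers unrelated and unlikely relationships. The time course "rules out a causal relationship and another cause (concomitant drugs, therapies, complications, etc) is suspected".

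Below the two categories the section adds: "The definition implies a reasonable possibility of a causal relationship between the event and the study drug". It then lists factors to weigh, among them concomitant drugs and underlying disease: "Each report should be evaluated in the context of the natural history and course of the disease being treated".

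Protocol Section 8.1.1 sets the threshold for an adverse drug reaction differently. It asks only that the causal "relationship between a medicinal product and an AE is at least a reasonable possibility, ie the relationship cannot be ruled out".

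SAP Section 11.1 states: "An AE will be considered drug-related if the relationship attribution is" possible, probable or definite. It adds events whose attribution is missing, and later sets a missing relationship to the maximum, definite.

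**The concern.** Both categories in 8.1.3 join a timing condition to an other-cause condition, and both conditions must hold. The scale therefore does not cover every event. The uncovered case that matters is an event whose timing fits the study drug and for which another explanation also exists.

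That case is easy to envisage here. The indication in Protocol Section 3.2 is "management of NCFB subjects with chronic respiratory infections associated with" *P. aeruginosa*, so every subject has a lung disease that can produce respiratory symptoms. Cohort B subjects also take an inhaled antibiotic (Section 5.1). The potential risks named for the drug in Section 1.3.2.2 include irritation of the airways, and most of the solicited diary symptoms in Section 7.7 are respiratory.

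The causality call is used in:

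- the sentinel gate in Section 3.1, which looks for treatment-related AEs of Grade 2 or above in the first two subjects;
- the 24-hour notice to the Medical Monitor of related AEs of Grade 3 or above (Section 3.1.1);
- two of the three individual hold criteria (Section 4.3.1);
- two of the three ad hoc DSMB triggers (Section 4.3.2);
- the drug-related TEAE tables (SAP Section 11.1).

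**Working it through.** No arithmetic is involved, and the plan states no figure to reproduce. The check crosses the two conditions of 8.1.3 and compares each combination with 8.1.1.

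| Time course | Other cause | 8.1.3 gives | 8.1.1 gives | Result |
|---|---|---|---|---|
| Compatible | None | Yes | Reaction | Agree |
| Compatible | Present | Neither | Reaction, since not ruled out | **Conflict** |
| Rules out a link | Present | No | Not a reaction | Agree |
| Rules out a link | None | Neither | Not a reaction | Gap, answer obvious |

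Two of the four combinations have no category. Only the second row contradicts 8.1.1. In the fourth, 8.1.1 already settles the answer.

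The table treats a suspected and an identified cause as the same thing. The protocol uses the stronger word for Yes and the weaker for No. If an alternative is merely suspected and cannot be identified, a lenient reader could still choose Yes, which narrows the second row without closing it.

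Next, follow a second-row event through the plan under each way it might be coded.

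| Coded as | Sentinel gate, attribution-based holds and DSMB triggers | Drug-related TEAE tables |
|---|---|---|
| Yes | Counts, if the grade or seriousness condition is met | Counted |
| No | Does not count | Not counted |
| Blank | No rule given | Counted as definitely related |

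The same facts can thus give opposite tabulations. The SAP rule for missing attribution works at the analysis stage and does not reach decisions made while dosing is under way. The holds and DSMB triggers that depend on attribution also call for confirmation by unblinding. That step shows which product was given. It does not recover an event already judged unrelated.

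Finally, does the rest of 8.1.3 repair the conflict? The reasonable-possibility sentence describes what the definition implies and leaves the no-other-cause condition in place. The listed factors direct the investigator to look for underlying disease and concomitant drugs, and finding either one defeats a literal Yes. Placing possible relationships under a rule that demands no alternative makes 8.1.3 inconsistent within itself as well as with 8.1.1.

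**The case against.** The best defence is that 8.1.3 already points to the 8.1.1 standard. Yes includes possible relationships, the next paragraph speaks of a reasonable possibility, and weighing other causes would be largely redundant if any alternative ended the assessment. Many investigators may well apply the lower threshold. This stands as a limit on the practical effect. It does not remove the condition from the text.

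A reader might infer more than the documents support in five ways.

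- **That the text itself causes under-attribution.** It does not. No requires timing that excludes a link, so on a literal reading the second-row event is unclassified. Under-attribution arises only if an investigator, left without a category, chooses No. A blank moves the tables the other way.
- **That most respiratory events are affected.** The documents give no AE rates. Subjects must be free of acute infection or exacerbation before the first dose (inclusion criterion 10), pre-existing conditions become AEs only if they change (Section 8.1), and Cohort B antibiotics have been taken for at least 3 months. How often an alternative cause would be named is unknown.
- **That the safeguards would rarely fire.** Several need no attribution: the bronchospasm criterion in Section 4.3.1, the unacceptable-toxicity trigger in 4.3.2, management of acute post-dose AEs and unblinded DSMB review of all available data in 3.1.1, continuing Medical Monitor review in 4.3, and reporting of all SAEs up to 30 days after the last dose in 8.3. All TEAEs are also tabulated by treatment group whatever their relationship.
- **That SUSAR reporting is suppressed.** SUSARs are adverse reactions, and 8.1.1 defines a reaction at the lower threshold. The two sections disagree, but the documents do not show that the stricter one would govern.
- **That the eCRF conflicts with the SAP.** The labels in 8.1.3 and SAP 11.1 match, and the eCRF is not among the documents.

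**Conclusion.** Wrong as written. This is a stated rule that contradicts the protocol's own threshold for a reaction, so it is more than missing detail. One of the four combinations is in direct conflict with 8.1.1, and one further combination has no category but an obvious answer.

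The consequence is inconsistent coding of the same event between investigators. An event forced to No is under-attributed and is not counted at the sentinel gate, in two of three hold criteria or in two of three ad hoc DSMB triggers. The sentinel gate deserves most attention, because its own wording offers no route that does not depend on attribution.

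The number of events affected cannot be derived from the documents, and the attribution-free safeguards bound the harm. The conclusion rests on the text of 8.1.1, 8.1.3 and SAP 11.1 alone. It assumes that investigators may apply 8.1.3 as worded and that no training or completion guideline outside these documents already corrects it.

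**What to change.** Reconcile Section 8.1.3 with Section 8.1.1:

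- delete the condition that no other cause can be identified;
- define Yes as a causal relationship that is at least a reasonable possibility, meaning it cannot be ruled out, even if another cause is also possible;
- define No as a relationship that can be ruled out.

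The two categories are then exhaustive and rest on the protocol's own standard. Underlying disease and concomitant drugs stay as factors to weigh in reaching the judgement. When the text is amended, check that the eCRF offers the categories that SAP Section 11.1 expects.

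The cost is a wording amendment, with a matching eCRF change if that check shows one is needed. Design, sample size and dosing are untouched. The downside is that the count of drug-related AEs may rise somewhat.
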